## CLINICAL TRIAL PROTOCOL SYNOPSIS

Name of company: Boehringer Ingelheim		Tabulated Trial Protocol			
Name of finished product: Not applicable					
Name of active ingredient: BI 836845					
Protocol date: 13 December 2013	Trial number: 1280.4		Revision date: 30 March 2016		
Title of trial: A Phase Ib/II Randomized Study of BI 836845 in Combination with Exemestane and Everolimus Versus Exemestane and Everolimus Alone in Women with Locally Advanced or Metastatic Breast Cancer					
Co-ordinating Investigator:					
	
Phone: + [REDACTED] Fax: + [REDACTED]
				
Trial site(s):	Multicenter trial, international				
Clinical phase:	Ib/II				
Objective(s):	
Phase I part: To determine the maximum tolerated dose (MTD) and recommended Phase II dose of BI 836845 in combination with exemestane and everolimus in women with HR+/HER2- locally advanced or metastatic breast cancer
 
Phase II part: To evaluate the anti-tumor activity of BI 836845 in combination with exemestane and everolimus versus exemestane and everolimus alone in women with HR+/HER2- locally advanced or metastatic breast cancer
 
In addition, safety will be assessed
				
Methodology:	
Open label, multicenter study in two parts:
 

Phase I – single arm, dose escalation with BI 836845 + everolimus + exemestane

Phase II – two arms, randomized, parallel design; arm 1: everolimus + exemestane ; arm 2: BI 836845 + everolimus + exemestane

				
No. of patients:	
total entered: Between 171 and 198
 
each treatment: Phase I: about 21–48; Phase II: approximately 75 patients per treatment arm (2-arm study)
				
Diagnosis :	HR+/HER2- locally advanced or metastatic breast cancer				

Proprietary confidential information.

© 2016 Boehringer Ingelheim International GmbH or one or more of its affiliated companies. All rights reserved.  
This document may not - in full or in part - be passed on, reproduced, published or otherwise used without prior written permission.

Name of company: Boehringer Ingelheim		Tabulated Trial Protocol		
Name of finished product: Not applicable				
Name of active ingredient: BI 836845				
Protocol date: 13 December 2013	Trial number: 1280.4		Revision date: 30 March 2016	
Main criteria for inclusion: Histologically-confirmed locally advanced or metastatic breast cancer not deemed amenable to curative surgery or curative radiation therapy Tumors are positive for estrogen-receptor (ER) and/or progesterone receptor (PgR); HER2 negative Postmenopausal women Disease refractory to non-steroidal aromatase inhibitors Objective evidence of recurrence or progression on or after the last systemic therapy prior to the study entry Patients must have a measurable lesion according to RECIST version 1.1 or bone lesion <del>only</del> : lytic or mixed (lytic + sclerotic) in the absence of measurable lesion				
Test product(s): BI 836845 dose: Phase I: 750 mg weekly as starting dose; Phase II: RP2D as established in Phase I mode of admin.: Intravenous infusion over 60 minutes				
Comparator products: Exemestane plus Everolimus dose: Exemestane: 25 mg per day Everolimus: Phase I: 10 mg per day as starting dose; Phase II: Arm 1: 10 mg per day, Arm 2: RP2D as established in Phase I mode of admin.: Oral				
Duration of treatment: Continuous treatment until disease progression, intolerable AEs, consent withdrawal or non-compliance with the study protocol				

Proprietary confidential information.

© 2016 Boehringer Ingelheim International GmbH or one or more of its affiliated companies. All rights reserved.

This document may not - in full or in part - be passed on, reproduced, published or otherwise used without prior written permission.

Name of company: Boehringer Ingelheim		Tabulated Trial Protocol		
Name of finished product: Not applicable				
Name of active ingredient: BI 836845				
Protocol date: 13 December 2013	Trial number: 1280.4		Revision date: 30 March 2016	
Criteria for efficacy: The primary endpoint of the phase II part of this study is progression-free survival, as determined by RECIST 1.1. Secondary endpoints are: 

• Time to progression

• Objective response (CR, PR)

• Time to objective response

• Duration of objective response

• Disease Control (CR + PR + SD24w + Non-CR/Non-PD24w)

• Duration of disease control

				
Criteria for safety: The primary endpoints of the phase I part of this study are occurrence of dose limiting toxicity and determination of MTD. Other safety endpoints including incidence and intensity of adverse events according to the Common Terminology Criteria for Adverse Events (CTCAE) Version 4.03, laboratory tests, physical examination, ECOG performance score, electrocardiogram (ECG) and vital signs				
Statistical methods: Descriptive statistical analysis; exploratory design				

Proprietary confidential information.

© 2016 Boehringer Ingelheim International GmbH or one or more of its affiliated companies. All rights reserved.  
This document may not - in full or in part - be passed on, reproduced, published or otherwise used without prior written permission.

## FLOW CHART

## **FLOW CHART – PHASE I PART**

Proprietary confidential information.

© 2016 Boehringer Ingelheim International GmbH or one or more of its affiliated companies. All rights reserved.

This document may not - in full or in part - be passed on, reproduced, published or otherwise used without prior written permission.

- a Screening: The screening visit should be performed within 28 days prior to first drug administration (Day -7 of Run-in). Safety lab at the screening assessment can serve as the Day -7 pre-treatment assessment of Run-in period if performed within 72 hours before the first treatment and does not need to be repeated
- b Run-in: Consists of 7 days. During the run-in period, patients should take daily everolimus and exemestane treatment.
- c Treatment courses: All courses are 4 weeks in duration (28 days). All subsequent visit dates should be calculated based on Course 1 Visit 1 date. One or more visits can be skipped in case of treatment interruption. Refer to [Section 6.2.2](#). Patients may continue on treatment until the criteria for stopping medication are met (see [Section 3.3.4](#)).
- d EOTV: End of Treatment visit. If the decision to permanently discontinue all study treatments is taken during a scheduled visit, the End Of Treatment Visit (EOTV) should be performed instead of the scheduled visit (within 7 calendar days after last drug administration)
- e FU: All patients should have a follow-up visit 42 days (+7days) after the permanent discontinuation of the study drugs

1. Written informed consent must be obtained before any protocol specific screening assessment is performed
2. Physical exam: includes a thorough cardiopulmonary, abdominal and lymph node exam and an assessment of the mental and neurological status
3. Vital signs: includes respiratory rate, pulse, temperature and blood pressure
4. 12-lead ECG: 12-Lead resting digital electrocardiogram (ECG) are recorded digitally and in triplicate. ECG will be performed at Screening, EOTV and FU. ECG will be repeated at Visit 1/Day 1, Visit 3/Day 8 and Visit 4/Day 15 of Course 1; Visit 1/Day 1 and Visit 3/Day 15 of Courses 2, 3; and at Visit 1/Day 1 of Courses 6,9,12, etc.. ECG should be performed prior to and immediately after the end of BI 836845 infusion. PK samples will be taken immediately after ECG recording. See [Section 5.2.4](#).
5. Safety labs: include hematology (CBC), coagulation and biochemistry. Urinalysis only at screening and EOTV. Fasting blood test is required for metabolic panels. See [Section 5.2.3](#) for detail. No need to repeat the safety lab on Day -7 of Run-in if within three calendar days of the screening safety lab and the patient is deemed stable by the investigator. Safety lab can be performed one day prior to the scheduled test. Unscheduled safety lab should be performed if clinically indicated and documented in the eCRF
6. HBV and HCV profile: All patients should be screened for hepatitis B and hepatitis C. Hepatitis B and C lab screen should include HBV-DNA and/or HBsAg, anti-HCV Ab and/or HCV RNA-PCR (local lab)
7. Archival tumor tissue collection: the most recent/appropriate archival tumor tissue must be collected prior to the start of run-in. Refer to [Appendix 10.7](#) for tissue requirements

8. **Everolimus and exemestane drug intake starting from Day -7 of Run-in and up to Course 1 Visit 3 Day 8 must be recorded in the patient diary card. The diary card should be returned on Day 1 and Day 8 of Course 1.**
9. **Immunogenicity (ADA):** On days when BI 836845 is dosed, ADA samples are to be collected prior to BI 836845 infusion. ADA samples must be collected at Courses 1 through 12, EOTV and at the FU visit. For detailed sampling schedule, refer to Appendix 10.5
10. **Tumor assessments:** Tumor assessments should include CT or MRI scans of the chest, abdomen and pelvis, and, if clinically indicated, any other known or suspected sites of disease (e.g. breast, neck, brain etc.) according to RECIST 1.1. After study entry, all lesions identified as target and non-target lesions during the screening should be followed up at all prespecified imaging time points. The same radiographic procedure must be used throughout the study. Bone scans should be performed at screening (see [Section 5.1.2](#) for more detail).  
Assessment will be performed at the following time points until progression/start of further treatment (tumor assessments after start of BI 836845 should be performed no more than 7 days prior to the scheduled tumor assessment date up to week 48 AND no more than 14 days prior to the scheduled tumor assessment date after week 48):
  - At screening (within 28 days prior to starting of treatment)
  - Every 8 weeks: during week 8 (49-56 days after start of BI 836845), during week 16 (105-112 days after start of BI 836845), during week 24 (161-168 days after start of BI 836845), during week 32 (217-224 days after start of BI 836845), during week 40 (273-280 days after start of BI 836845), during week 48 (329-336 days after start of BI 836845)

Proprietary confidential information.

- Every 12 weeks after week 48 (e.g. during week 59-60 (406 – 420 days after start of BI 836845), during week 71-72 (490 – 504 days after start of BI 836845), etc.)  
In the event of an interruption/delay to treatment, the tumor assessment schedule should not be changed.  
Patients who discontinue the trial for any reason other than imaging based progressive disease should have a tumour assessment (RECIST 1.1) performed at EOTV. Except in case of discontinuation from treatment due to imaging based progression, tumor assessment at EOTV is not necessary if the previous evaluation was done within 4 weeks of EOTV  
Unscheduled scan based on the investigator's judgement is allowed and should also be documented in eCRF
- 16. Everolimus should be dispensed through IRT. The prescription of exemestane should be filled by pharmacy.  
Patient's screening, run-in, all drug dispensation visits and EOTV will be collected in the IRT system
- 17. Compliance check: on Day 1 of every course and at EOTV
- 18. For Course 2 only

## FLOW CHART – PHASE II PART

Study period	Screening (a)	Treatment Courses (c)								EOT V (d)	FU1 (f)	Add. FU (f)	O P (g)
	SCR	Course 1				Course 2 Onwards							
Visits (V)		1	2	3	4	1	2	3	4				FU2-FUn
Days	- 28 to -1	1 ±2	8 ±2	15 ±2	22 ±2	1 ±2	8 ±2	15 ±2	22 ±2				
Informed consent (1)	X												
Randomization (2)		X											
Demographics	X												
Medical history	X												
Inclusion/ exclusion	X	X											
Physical exam(3)	X	X					X				X	X	
Height	X												
Body weight	X	X					X				X	X	
Vital sign (4)	X	X	X	X	X	X	X				X	X	
ECOG	X	X					X				X	X	
12- lead ECG (triplicate) (5)	X	X	X	X		X					X	X	
Safety lab (6)	X	X		X		X				X (18)		X	X
HBV, HCV profile (7)	X												
Archival tumor tissue collection (8)	X												
Blood sample for companion diagnostic development (21)		X											
			█		█					█			
			█										
			█			█				█			
			█		█		█			█			
			█		█		█			█			
			█			█				█			
			█				█			█			
			█					█		█			
			█						█	█			
			█							█			
Tumor assessment and bone scan by RECIST 1.1 (15)	X	See schedule below (15)											
Adverse event		X	X	X	X	X	X	X	X	X	X	X	
Concomitant therapy	X	X	X	X	X	X	X	X	X	X	X	X	
Dispense/fill EVE+ EXE(16)		X			X								
Compliance check (17)					X					X			
EVE+ EXE treatment		Once daily continuous											
BI 836845 i.v. Arm 2 only(23)		X	X	X	X	X	X	X	X				
Termination of study medication										X			
Completion of the Phase II part (19)											X (19)	X (19)	
Collection of information on disease status and further therapies (20)													X

Proprietary confidential information.

© 2016 Boehringer Ingelheim International GmbH or one or more of its affiliated companies. All rights reserved.

This document may not - in full or in part - be passed on, reproduced, published or otherwise used without prior written permission.

- a Screening: The screening visit should be performed within 28 days prior to first drug administration. Safety lab at the screening assessment can serve as the Day 1 pre-treatment assessment of Course 1 if performed within 72 hours before the first treatment and does not need to be repeated.
- c Treatment courses: All courses are 4 weeks in duration (28 days). All subsequent visit dates should be calculated based on Course 1 Visit 1 date. One or more visits can be skipped in case of treatment interruption. Refer to [Section 6.2.2](#). Patients may continue on treatment until the criteria for stopping medication are met (see [Section 3.3.4](#)).
- d EOTV: If the decision to permanently discontinue all study treatments is taken during a scheduled visit, the End Of Treatment Visit (EOTV) should be performed instead of the scheduled visit (within 7 calendar days after last drug administration)
- f FU1 and Additional FU: All patients should have a follow-up 1 (FU1) visit 42 days (+7days) after the permanent discontinuation of study drugs. Patients who have not progressed and not started further treatment at FU1 should have additional limited follow-up visits at scheduled tumor assessment until progression, start of further anti-cancer treatment, consent withdrawal, lost to follow-up or death. See [Section 6.2.3](#)
- g OP: observation period every  $90 \pm 15$  days after the last follow-up visit (visit or phone contact allowed)
- h On Visits 2 and 4 of Courses 3 through 6, and on Visits 2, 3, 4 from Course 7 onwards, the study visit for patients on arm 1 (everolimus + exemestane) can be conducted via phone for collection of adverse events and concomitant medication

1. Written informed consent must be obtained before any protocol specific screening assessment is performed. Additional informed consent must be obtained prior to fresh tumor biopsy
2. Randomization: the randomization may take place up to 3 days prior to the C1V1 if site procedures require advance randomization to accommodate the logistics of dispensing study medication to patients. Sites that use this option must include a copy of site policy or documented justification in the ISF and submit a copy to the sponsor. If randomization is performed prior to C1V1, the subsequent visits must be scheduled with reference to C1V1. Arm 1 treatment: everolimus + exemestane; Arm 2 treatment: BI 836845 + everolimus + exemestane. Patient's screening, randomization and EOTV will be collected in the IRT system
3. Physical exam: includes a thorough cardiopulmonary, abdominal and lymph node exam and an assessment of the mental and neurological status. No need to repeat the physical exam on C1V1D1 if within three calendar days of the screening physical exam and the patient is deemed stable by the investigator
4. Vital signs: includes respiratory rate, pulse, temperature and blood pressure
5. 12-lead ECG: 12-Lead resting digital electrocardiogram (ECG) are recorded digitally and in triplicate. ECG will be performed at Screening, EOTV and FU1. ECG will be repeated at Visit 1/Day 1, Visit 2/Day 8 and Visit 3/Day 15 of Course 1; Visit 1/Day 1 of Course 2; and at Visit 1/Day 1 of Courses 3, 6, 9, 12, etc. ECG should be performed prior to BI 836845 infusion and/or everolimus+ exemestane administration, and immediately after BI 836845 infusion (for arm 2 patients) OR one hour after the administration of everolimus+ exemestane (for arm 1 patients). See [Section 5.2.4](#)
6. Safety labs: include hematology (CBC), coagulation and biochemistry. Urinalysis only at screening and EOTV. Fasting blood test is required for metabolic panels. See [Section 5.2.3](#) for detail. No need to repeat the safety lab on C1V1D1 if within three calendar days of the screening safety lab and the patient is deemed stable by the investigator. Safety lab can be performed one day prior to the scheduled test. Unscheduled safety lab should be performed if clinically indicated and documented in the eCRF
7. HBV and HCV profile: All patients should be screened for hepatitis B and hepatitis C. Hepatitis B and C lab screen should include HBV-DNA and/or HBsAg, and anti-HCV Ab and/or HCV RNA-PCR (local lab)
8. Archival tumor tissue collection: the most recent/appropriate archival tumor tissue must be collected prior to C1V1 treatment. Refer to [Appendix 10.7](#) for tissue requirements

Proprietary confidential information.

14. Immunogenicity (ADA): ADA sampling is mandatory only for patients receiving BI 836845 containing regimen in arm 2. On days when BI 836845 is dosed, ADA samples are to be collected prior to BI 836845 infusion. ADA samples must be collected at Courses 1 through 12, EOTV and FU1 visit. For detailed sampling schedule, refer to [Appendix 10.5](#)

15. Tumor assessments should include CT or MRI scans of the chest, abdomen and pelvis, and, if clinically indicated, any other known or suspected sites of disease (e.g. breast, neck, brain etc.) according to RECIST 1.1. After study entry, all lesions identified as target and non-target lesions during the screening should be followed up at all prespecified imaging time points. The same radiographic procedure must be used throughout the study, and during the phase II part of the trial imaging guidelines should be observed. Bone scans should be performed at screening (see [Section 5.1.2](#) for more detail).

Assessment will be performed at the following time points until progression/start of further treatment (tumor assessments after randomisation should be performed no more than 7 days prior to the scheduled tumor assessment date up to week 48 AND no more than 14 days prior to the scheduled tumor assessment date after week 48):

- At screening (within 28 days prior start of treatment):
- Every 8 weeks: during week 8 (49-56 days after randomisation), during week 16 (105-112 days after randomisation), during week 24 (161-168 days after randomisation), during week 32 (217-224 days after randomisation), during week 40 (273-280 days after randomisation), during week 48 (329-336 days after randomisation)
- Every 12 weeks after week 48 (e.g. during week 59-60 (406 – 420 days after randomisation), during week 71-72 (490 – 504 days after randomisation), etc.)

In the event of an interruption/delay to treatment, the tumor assessment schedule should not be changed. Patients who discontinue the trial for any reason other than imaging based progressive disease should have a tumour assessment (RECIST 1.1) performed at EOTV. Except in case of discontinuation from treatment due to imaging based progression, tumor assessment at EOTV is not necessary if the previous evaluation was done within 4 weeks of EOTV

Unscheduled scan based on the investigator's judgement is allowed and should also be documented in eCRF

16. Everolimus, if supplied by the sponsor, should be dispensed through IRT. The prescription of everolimus (if not supplied by the sponsor) and exemestane should be filled by pharmacy. Patient's screening, randomization, all drug dispensation visits and EOTV will be collected in the IRT system

17. Compliance check: on Day 1 of course 2, 3, 4, 5, etc. and at EOTV

18. For Course 2 only

19. Completion of the phase II part: Completion of the phase II part of the study should be recorded at FU (the last FU visit) when PD/death occurs, starting of new treatment, consent withdrawal or death

20. Collection of information on disease status and further therapies: information on progression, further anti-cancer treatment and death should be collected from patient's notes or by telephone contact with the patient. A formal study visit is not required

21. At visit C1V1D1 of the Phase II part, 3 mL of blood will be taken before any treatment is administered in both Arms 1 and 2. The samples will be used for future companion diagnostic development needs or for measurement of other putative predictive biomarkers in serum.

22. [REDACTED]

23. If extremely necessary, for arm 2 patients receiving BI 836845 infusion at a subsequent visit, the transaction with the IVRS/IWRS system can be done up to one day before the actual visit date. Please refer to BI 836845 Preparation Storage and Administration instructions for more information about BI 836845 stability and storage conditions once diluted in the infusion bag.

24. On Course 5 Day 1 only (After 16 weeks of treatment)

Proprietary confidential information.

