### Phase II part:

Once the RP2D is determined (see [Section 5.2.7](#)), an open-label, two-arm randomized Phase II study will commence to further assess the anti-tumor activity of BI 836845 in combination with exemestane and everolimus in women with HR+/HER2- locally advanced or metastatic breast cancer. Eligible patients will be randomly assigned in 1:1 ratio to one of the two treatment arms as listed below. Each arm will enroll approximately 75 patients (total of approximately 150 patients). Randomization will be stratified by visceral involvement (yes vs. no). Visceral involvement refers to lung, liver, brain, pleural and peritoneal metastasis.

Treatment arms for the Phase II part are as the following:

**Arm 1 (control arm):** Once daily everolimus 10 mg plus once daily exemestane 25 mg orally

**Arm 2 (experimental arm):** BI 836845 and everolimus plus exemestane. BI 836845 will be administered intravenously once weekly, exemestane is dosed at 25 mg once daily. The treatment doses of BI 836845 and everolimus will be that of the RP2D from the Phase I part of the study

Patients will receive continuous daily treatment of everolimus plus exemestane with or without weekly infusions of BI 836845.

[figure not shown]
Proprietary confidential information.

© 2016 Boehringer Ingelheim International GmbH or one or more of its affiliated companies. All rights reserved.

This document may not - in full or in part - be passed on, reproduced, published or otherwise used without prior written permission.

The end of treatment visit (EOTV) should be performed when the study treatment is permanently discontinued followed by a Follow-up visit (FU1) 42 days after the termination of all study medications. Patients who discontinue study drug for reasons other than disease progression may continue the scheduled tumor assessments according to the [Flow Chart](#). The last follow-up visit will be defined as the last visit of on-study period for this trial. Afterwards, patients will be monitored for vital status in the Observation Period. Adverse events occurring from the date when informed consent is obtained until the start of observation period will be collected.

The Phase II part of the trial will be concluded as soon as the last patient has completed the first Follow-up Visit (FU1).

\* For patients who discontinue study drugs without disease progression

Figure 3.1: 2 Study diagram – Phase II Part

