Blood samples for biomarkers, PK and immunogenicity (for patients on arm 2 only) will be collected before (-0.05h) the administration of BI 836845 and/or everolimus plus exemestane. Furthermore, for patients having a biopsy, in addition to fresh tumor biopsy, blood samples for biomarkers (for all patients) and PK (for arm 2 patients only) should also be collected before the biopsy tumor sample is obtained (but not earlier than one hour before the biopsy). ECG will be collected from all patients, prior to trough PK sampling and administration of any study drug, and immediately after the end of BI 836845 infusion (for patients receiving BI 836845).

Proprietary confidential information.

© 2016 Boehringer Ingelheim International GmbH or one or more of its affiliated companies. All rights reserved.

This document may not - in full or in part - be passed on, reproduced, published or otherwise used without prior written permission.

BI 836845) OR one hour after the administration of everolimus + exemestane (for patients not receiving BI 836845).

*Course 1, Visit 4 (22 ± 2 Days after CIV1)*

BI 836845 should be administrated for patients on arm 2. Vital signs, adverse events and concomitant medication should be collected from all patients.

*Course 2 (Day 1, 8, 15, 22 ± 2 Days) and all subsequent visits*

Refer to [Flow Chart](#) and Appendix 10.5 Tables [10.5.1: 1 – 10.5.1: 2](#) for details.

For patients on arm 1 (everolimus + exemestane) of the Phase II part, the study visits on Visits 2 and 4 of Courses 3 through 6, and on Visits 2, 3, 4 from Course 7 onwards can be conducted via phone for the collection of adverse events and concomitant medication.

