### 7.3 PLANNED ANALYSES

During the Phase I part, cohorts of patients treated with BI 836845 in combination with exemestane and everolimus will be evaluated continuously based on the totality of the safety data available in order to determine the recommended phase II dose.

Efficacy analysis will include all randomised patients in the Phase II part. For the Phase I dose finding stage, PFS and objective tumor response will be summarized descriptively by cohort. No comparison will be done between cohorts.

Safety analysis will be summarized separately for patients treated in the Phase I and Phase II part of the trial. The safety profile of the Phase II part will be compared in a descriptive manner between the experimental and the control arm.

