2) AEs with onset after 9th of December 2016

This includes the following patients:

- Patients who stopped xentuzumab on 28th of October 2016 due to sponsor's decision, i.e. AEs with onset date after 9th of December 2016 will be considered.
- Patients receiving everolimus and exemestane only, i.e. AEs with onset date after 9th of December 2016 will be considered.

Both parts will be analyzed by treatment and a total column will be given.

Proprietary confidential information © 2018 Boehringer Ingelheim International GmbH or one or more of its affiliated companies

For the Phase II part all AEs occurring before first drug intake will be assigned to 'screening' and all AEs occurring after the REP will be assigned as 'post-treatment'.

AEs will be displayed by the initial dose of study medication administered on the first day of treatment (or planned to be administered, for the run-in period of the Phase Ib part).

An overall summary of AEs will be presented. The frequency of patients with AEs will be summarised by treatment, primary system organ class (SOC) and preferred term (PT).

Separate tables will be provided for patients with drug-related AEs, AEs leading to dose reduction, AEs leading to discontinuation, serious adverse events (SAE), serious drug-related AEs, AEs leading to death, other significant AEs, adverse events of special interest (AESI), and AEs fulfilling the DLT definition (for phase Ib part only). For the Phase II part an overall summary of AEs as well as a table for AEs and SAEs by treatment will be provided for the subgroups of visceral involvement.

Sorting order:

In tables presenting SOC and PT, SOCs will be sorted alphabetically and PTs (within SOC) by descending frequency.

Reporting of CTCAE grades in tables:

In tables showing AEs by worst CTCAE grade, AEs with missing CTCAE grade will only be displayed under the category "All grades", but no category "Missing grade" will be displayed. Therefore the categories "Grade 1" to "Grade 5" might not add up to the category "All grades"; a footnote will explain this handling.

Displaying of CTCAE grades in AE tables (Section 15) will be "All grades", "Grade 1", "Grade 2", "Grade 3", "Grade 4", and "Grade 5" separately. In the appendix (Section 16.1.9.2), the categorisation "All grades", "Grade 1/2", "Grade 3/4/5", will be used.

Listings of AEs

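### From Course 3 only Arm 1 may have phone visits, so arm differences in low-grade, examination-based AEs from then on may partly reflect how AEs were collected, and SAP 7.8.1 has no table by onset period to show it

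*Protocol*

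**What the plan says.** **Visits.** Both Phase II arms have four weekly visits per 28-day course, and AEs are collected at each. Footnote h of the Phase II flow chart makes an exception for the control arm. It says that "the study visit for patients on arm 1 (everolimus + exemestane) can be conducted via phone for collection of adverse events and concomitant medication". The exception covers the second and fourth visits of Courses 3 to 6, and every visit except the first in Course 7 and later. Protocol 6.2.2.2 repeats the rule for the same visits: they "can be conducted via phone for the collection of adverse events and concomitant medication". Courses 1 and 2 have no phone option. In Arm 2, "BI 836845 will be administered intravenously once weekly" (protocol 3.1), and protocol 4.1.4.1.1 places the infusion at the investigator site. Protocol 4.4.2 requires close medical supervision and recommends an hour of observation afterwards, adjustable if Course 1 passes without a reaction.

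**Analysis.** Protocol 7.3: "The safety profile of the Phase II part will be compared in a descriptive manner between the experimental and the control arm". SAP 7.8.1 bases all AE analyses on the number of patients with an AE, and "The frequency of patients with AEs will be summarised by treatment, primary system organ class (SOC) and preferred term (PT". For Phase II it splits on-treatment AEs at 9 December 2016, which is the 28 October 2016 stop of xentuzumab plus the 42-day residual effect period. SAP 7.8.1 contains no AE table by course or onset period, no exposure-adjusted rate and no analysis by mode of contact.

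**The concern.** The frequency of AE questioning is the same in both arms throughout. What changes from Course 3, and only in Arm 1, is whether a clinician sees the patient when asking. A mouth lesion or mild rash that the patient does not mention can be noticed in clinic but not on the phone.

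The direction matters. Protocol 2.3 warns that blocking IGF signalling may aggravate everolimus toxicity, mucositis in particular, and supports this with a stomatitis contrast from other trials (16% against 36%). Stomatitis is one of the SAP's user-defined AE categories. If phone contact misses some low-grade events in Arm 1, the crude difference moves towards the signal that the protocol expects, in an open-label trial.

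Patients reach Course 3 on different dates, so a calendar split leaves comparable and non-comparable time mixed in the first part. From the planned tables a reader cannot tell whether an arm difference was already present while both arms were seen in clinic every week.

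**Working it through.** The plan gives no figure on this point. The only inputs are the visit rule and, as a stand-in for time on treatment, the control median PFS of 7.8 months in protocol 7.6. That section's rate reproduces: ln 2 / 7.8 = 0.0889, stated as 0.089.

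**1. Share of Arm 1 visits that may be by phone, by count.**

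| Courses | Phone-eligible / scheduled | Share |
|---|---|---|
| 1-2 | 0 / 8 | 0% |
| each of 3-6 | 2 / 4 | 50% |
| each from 7 | 3 / 4 | 75% |
| 1-6 | 8 / 24 | 33% |
| 1-9 | 8 + 9 = 17 / 36 | 47% |
| 1-12 | 8 + 18 = 26 / 48 | 54% |

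The Arm 2 share is 0% throughout, while infusions continue.

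**2. Weighted by time on treatment.** Assume exponential time on treatment. Week w (w = 0, 1, 2, ...) gets weight S(w) = exp(-λ × w × 7 × 12/365.25), with λ = ln 2 / median in months. The share is the sum of S(w) over phone-eligible weeks divided by the sum over all weeks.

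- Median 7.8 months: 6.39 / 20.38 = 31% over 26 weeks; 15.58 / 32.35 = 48% over 52 weeks.
- Median 5.5 months (an assumption, not in the documents): 5.56 / 18.53 = 30%; 12.25 / 27.25 = 45%.
- At 7.8 months, 85% of Arm 1 patients reach Course 3 (Day 57) and 61% reach Course 7 (Day 169). Of Arm 1 treatment time, 63% (26 weeks) to 77% (52 weeks) falls after Course 2; at 5.5 months, 61% to 73%.

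These are shares of eligible visits. They are not estimates of bias.

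**3. What the shares could do to an AE frequency.** Take the same true weekly first-event hazard h and the same 7.8-month median in both arms. Clinic detects every event, phone detects a fraction s, every eligible visit is a call, and a missed event is never recovered. Recorded incidence = Σ S(w) × U(w) × (1 - exp(-h × d(w))). Here d = s in phone-eligible Arm 1 weeks and 1 otherwise, and U(w) is the chance of no recorded event before week w. The last three columns give the Arm 2 minus Arm 1 gap in percentage points.

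| h | Arm 2 incidence | s = 0.9 | s = 0.75 | s = 0.5 |
|---|---|---|---|---|
| 0.005 | 19.9% | 0.9 | 2.2 | 4.6 |
| 0.01 | 33.2% | 1.2 | 3.0 | 6.4 |
| 0.02 | 50.0% | 1.2 | 3.1 | 6.9 |
| 0.05 | 71.7% | 0.7 | 1.9 | 4.4 |

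At s = 1 the gap is 0. For scale, with the planned 75 per arm the standard error of a difference, √(2p(1-p)/75), is 6.5 points at p = 0.2 and 8.2 points at p = 0.5.

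**4. Is there a period with the same mode?** Course 3 Visit 1 falls on Day 2 × 28 + 1 = 57 and is not phone-eligible. The first possible phone visit is Course 3 Visit 2, Day 64. AEs with onset on Days 1-56 are therefore first asked about at a scheduled clinic visit in both arms.

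**The case against.** The strongest reply is that nothing here shows a bias. Phone use is optional, AEs are asked about weekly in both arms, and no document gives a rate of phone use or of phone detection. If phone is 90% as good as clinic, the illustrated gap is at most 1.2 points, under one patient in 75 and far inside sampling error. All of this stands.

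A reader might infer that Arm 2 was formally examined more often. The schedule does not support that. From Course 2 the flow chart shows one physical examination, one body weight and one ECOG score per course, with no distinction by arm. Scheduled ECGs from Course 2 fall on Visit 1, which is never by phone, and protocol 2.3 plans monthly glucose and lipid checks without distinction by arm. Weight loss and metabolic AEs are therefore poor examples, and asthenia is largely reported by the patient. What Arm 1 can lose is incidental observation between remaining clinic visits, which are two weeks apart in Courses 3-6 and four weeks apart from Course 7.

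The SAP is also not without safeguards. It tabulates each CTCAE grade, gives SAEs, dose reductions and discontinuations their own tables, lists AE start days, and splits at 9 December 2016. After 28 October 2016 Arm 2 has no infusion visits, so the contrast in visit mode no longer holds in the same way. These points limit the concern to low-grade, examination-based events. They do not remove it, because grades are not crossed with onset period, listings are not a comparison, and the split is by date rather than course.

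**Conclusion.** The asymmetry is written into the protocol and SAP 7.8.1 does not address it. From Course 3, while xentuzumab was given, arm differences in low-grade, examination-based AEs such as stomatitis and rash may partly reflect the mode of collection. The size is unknown: zero if phone detects as well as clinic, roughly 2 to 3 points at 75% relative detection and 4 to 7 points at 50%. Those figures assume exponential time on treatment equal to PFS, full use of the phone option and no later recovery of missed events. They also ignore the truncation on 28 October 2016.

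Three stronger readings are tempting and not supported:

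- That the arm difference is in part an artefact. The documents show only that it could be.
- That the full-period tables should give way to Courses 1-2. That would discard 63% to 77% of Arm 1 treatment time (7.8-month median, 26 to 52 weeks) and could hide late toxicity. Courses 1-2 are also not identical between arms, since Arm 2 has supervised infusions and the trial is open-label.
- That this comparison feeds a decision to proceed. Protocol 7.6 and 7.3.4 tie sizing and signal thresholds to PFS, and xentuzumab had been stopped before the SAP revisions of 2017 and 2018. SAP 4.2 gives the report's purpose as documentation for future trials.

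Protocol amendment 3 and the table shells are not among the documents, so later changes to visits or outputs could not be checked.

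**What to change.** In SAP 7.8.1, keep the full-period Phase II tables and add supplementary tables by arm (AE overview, SOC/PT by CTCAE grade, user-defined AE categories) for two onset periods:

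- Courses 1-2, about Days 1-56, when neither arm has phone visits.
- Course 3 up to 9 December 2016.

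Footnote the second set with the Arm 1 phone option and the loss of Arm 2 infusion visits after 28 October 2016. Between-arm statements on low-grade AEs should refer to both periods, and a difference seen only from Course 3 should be described as possibly due to contact mode. Such a difference would remain ambiguous, because a true late drug effect would look the same. Exposure-adjusted rates alone would not separate the two.

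No new data are needed, since SAP 7.8.1 already derives AE start day from first treatment. The cost is extra table runs and fewer events per table.
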